6.2. Adverse Events

Treatment-emergent AEs will be summarized by system organ class and preferred term defined by MedDRA.

The following treatment-emergent AE summary tables will be provided for this study:

- Any AEs
- SAEs

- AEs with severe intensity
- AEs and SAEs that are reasonably related to study agent
- AEs leading to discontinuation of study agent
- Infusion reactions
- Infections and infections requiring oral or parenteral anti-microbial treatment
- Serious infections

In addition to the summary tables, a listing of subjects who died and listings of subjects with the following AEs will be presented: SAEs, AEs leading to discontinuation of study agent(s), anaphylactic reactions or serum sickness reactions, malignancy, tuberculosis, clinically important hepatobiliary events (defined as $ALT \ge 3 \times ULN$ and either bilirubin $\ge 2 \times ULN$ or occurrence of a serious adverse event in the hepatobiliary system-organ class), and demyelination.

Infusion reactions and infection:

- An infusion reaction is identified as any unfavorable or unintended sign that occurs during the infusion or within 1 hour of completion of the infusion. Infusion reactions are captured in the eCRF.
- An infection is identified as any AE that was recorded as an infection by the investigator on the eCRF.

Since safety should be assessed relative to exposure, the following summaries will be presented:

- Proportion of subjects receiving scheduled IV study agent administrations at each study agent administration visit.
- Summary of cumulative golimumab dose.

In addition, all AE summary tables will include average weeks of follow-up and average number of IV infusions.

6.3. Clinical Laboratory Tests

The laboratory parameters include but are not limited to the following:

Hematology: hemoglobin, hematocrit, neutrophils, lymphocytes, monocytes, eosinophils, platelets, and WBC count.

Chemistry: BUN/urea, creatinine, total bilirubin, alkaline phosphatase, ALT/SGPT, AST/SGOT, bicarbonate, sodium, potassium, calcium, albumin, chloride, phosphate, glucose, uric acid and total protein.

Laboratory results will be graded according to NCI-CTCAE version 4.03 or later. Note that toxicity grading for creatinine increase will be based on the NCI CTC v4.03 or later criteria, but limited only to the part based on the upper limit of normal (ULN), the other part, that is based on change from baseline, will not be used for toxicity grading. Generic normal ranges will be applied whenever reference ranges are not available.

17

NCI-CTCAE grades will be used in the summary of laboratory data (Grade 0-4). The proportion of subjects for select laboratory parameters with maximum Grades will be presented. In addition, the proportion of subjects with markedly abnormal laboratory results will also be provided. The subjects' maximum post-baseline ALT and AST will also be summarized by TB prophylaxis (TB prophylaxis, or no TB prophylaxis).

Levels of laboratory values that are considered to be markedly abnormal have been defined for each laboratory parameter in Attachment 3.

Boxplots will be used to describe the selected laboratory analyte at baseline and at each scheduled time point. The selected laboratory analytes are: WBC counts, neutrophils, hemoglobin, platelets, ALT, and AST.

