There were 2 subjects with ALT elevation to > 8×ULN but neither subject met the criteria for Hy's Law consistent with hepatotoxicity. Subjects were not receiving TB prophylaxis; one of the subjects had baseline ALT which was already abnormal. All subjects with LFT abnormalities were managed conservatively with changes in MTX dosing but one subject was discontinued for elevated LFTs.

The incidence of injections with injection-site reactions through Week 48 was 0.8%; there was one SAE report of serum sickness-like reaction in a subject randomized to placebo who resumed golimumab treatment.

For the most comprehensive nonclinical and clinical information regarding golimumab, refer to the latest version of the Investigator's Brochure and Addenda for SIMPONI (golimumab).

Although the CNTO148JIA3001 study did not meet its endpoints, when JIA ACR response rates were analyzed as observed data through Week 48 (using Week 0 as baseline and comparing drug/placebo effect at each visit through Week 48) the study showed the potential for efficacy that could be attained with SC golimumab in children with pJIA. Therefore, it lends support to the study of IV golimumab in subjects with pJIA who have an inadequate response to MTX.

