 - d. Platelets $\ge 140 \times 10^3 \text{ cells/}\mu\text{L}$ (SI: $\ge 140 \times 10^9 \text{ cells/L}$)
 - e. Serum transaminase levels not exceeding 1.2 x the upper limit of normal for the central laboratory:
 - Aspartate aminotransferase (AST)
 - \circ \leq 67 IU/L (girls, ages 2 to \leq 4)
 - \circ \leq 58 IU/L (girls, ages 4 to \leq 7)
 - $\circ \leq 48 \text{ IU/L (girls, ages 7 to 18)}$
 - \circ \leq 83 IU/L (boys, ages 2 to \leq 4)

- \circ \leq 71 IU/L (boys, ages 4 to \leq 7)
- $\circ \leq 48 \text{ IU/L (boys, ages 7 to 18)}$
- Alanine aminotransferase (ALT)
 - $\circ \leq 41 \text{ IU/L (girls, ages 2 to 18)}$
 - \circ \leq 41 IU/L (boys, ages 2 to \leq 10)
 - $\circ \le 52 \text{ IU/L (boys, ages 10 to 18)}$
- f. Serum creatinine not to exceed:
 - 0.5 mg/dL (SI: 44 μ mol/L; ages 2 to 5)
 - 0.7 mg/dL (SI: 62 μmol/L; ages 6 to 10)
 - 1.0 mg/dL (SI: 88 μmol/L; ages 11 to 12)
 - 1.2 mg/dL (SI: 106 μmol/L; ages ≥13)
- 16. Subjects must be up to date with all immunizations in agreement with current local immunization guidelines for immunosuppressed subjects before Week 0.
- 17. A parent or guardian should accompany the subject to each study visit until the subject reaches the age of 18 years.
- 18. The subject and his/her parent (if applicable) must be able to adhere to the study visit schedule, and understand and comply with other protocol requirements.
- 19. Subject must be willing and able to adhere to the prohibitions and restrictions specified in this protocol.
- 20. Each subject (or their legally acceptable representative) must sign an ICF indicating that he or she understands the purpose of and procedures required for the study and are willing to participate in the study. Assent is also required of children capable of understanding the nature of the study (typically 7 years of age and older and per local regulations) as described in Section 16.2.3, Informed Consent.

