11.7. Safety Analyses

Adverse Events

The verbatim terms used in the CRF by investigators to identify adverse events will be coded using the Medical Dictionary for Regulatory Activities (MedDRA). All reported adverse events with onset during the treatment phase (ie, treatment-emergent adverse events, and adverse events that have worsened since baseline) will be included in the analysis. For each adverse event, the percentage of subjects who experience at least 1 occurrence of the given event will be summarized by treatment group.

Summaries, listings, datasets, or subject narratives may be provided, as appropriate, for those subjects who die, who discontinue treatment due to an adverse event, or who experience a severe or a serious adverse event.

The following analyses will be used to assess the safety of subjects in this trial:

- The occurrence and type of AEs
- The occurrence and type of SAEs
- The occurrence and type of reasonably related AEs
- The occurrence of infusion reactions
- The occurrence of ANA and anti-dsDNA antibodies
- The occurrence of antibodies to golimumab
- The occurrence of markedly abnormal laboratory (hematology and chemistry) parameters

Clinical Laboratory Tests

Laboratory data will be summarized by type of laboratory test. Reference ranges and markedly abnormal results (specified in the Statistical Analysis Plan) will be used in the summary of laboratory data. Changes from baseline results will be presented in pre- versus posttreatment cross-tabulations (with classes for below, within, and above normal ranges). Frequency tabulations of the abnormalities will be made. A listing of subjects with any markedly abnormal laboratory results will also be provided.

Vital Signs

Descriptive statistics of pulse/heart rate, respiratory rate, temperature, and blood pressure (systolic and diastolic) values and changes from baseline will be summarized at each scheduled time point in the Schedule of Events.

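### SAP 6.3 omits the laboratory cross-tabulation and listing that protocol 11.7 promises, and its maximum-grade summary has no baseline grade to separate entry abnormalities from new ones

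*SAP*

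**What the plan says.** Protocol 11.7, under clinical laboratory tests, states: "Changes from baseline results will be presented in pre- versus posttreatment cross-tabulations". The classes are below, within and above the normal range. The same paragraph adds: "A listing of subjects with any markedly abnormal laboratory results will also be provided". Protocol section 11 leaves the specific details to the SAP.

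SAP 6.3 grades laboratory results by NCI-CTCAE and specifies four displays:

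- For grades: "The proportion of subjects for select laboratory parameters with maximum Grades will be presented".
- For extreme values, using Attachment 3: "the proportion of subjects with markedly abnormal laboratory results will also be provided".
- For transaminases: "maximum post-baseline ALT and AST will also be summarized by TB prophylaxis".
- Boxplots at baseline and each scheduled visit for WBC, neutrophils, hemoglobin, platelets, ALT and AST.

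SAP section 6 says in general terms that changes in laboratory parameters will be examined. Neither 6.3 nor any other SAP section specifies a cross-tabulation, a shift table or a listing of markedly abnormal results. For creatinine, the part of the grading that depends on change from baseline is expressly not used.

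On entry, protocol inclusion criterion 15 requires "Serum transaminase levels not exceeding 1.2 x the upper limit of normal", and sets hemoglobin floors of 80, 85 or 90 g/L by age and sex.

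**The concern.** With one arm, each child's own baseline is the only internal comparator for laboratory safety. The children are on background methotrexate, and the entry limits admit some values that are already outside normal. A child who enters with a mildly raised ALT and does not change will appear in the maximum-grade table with a grade. So will a child who was normal at entry and rose to the same level, and the table cannot distinguish them. Because the sentence does not restrict the maximum to post-baseline values, it could even be programmed to count a child whose worst value came before the first infusion.

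The rest of the safety plan does account for baseline. Adverse events are treatment-emergent (SAP 6.2), vital signs are shown as changes from baseline (6.4), and ANA and anti-dsDNA are shown as baseline status and change in status (6.6). Graded laboratory results have no equivalent. At stake is whether the reader of that table can attribute mild abnormalities to the study period or to the condition at entry.

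**Working it through.** The plan gives no figure to reproduce on this point. The check sets the two documents side by side, tests whether the other displays fill the gap, and shows how carry-in would act.

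**1. Promised against specified**

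| Protocol 11.7 | SAP 6.3 |
|---|---|
| Cross-tabulation before and after treatment, by normal-range class | Not specified |
| Frequency of abnormalities | Maximum grade; proportion markedly abnormal |
| Listing of markedly abnormal results | Not specified (proportion only) |

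SAP Amendment 1 is dated 1 August 2018. Protocol Amendment 4, dated 16 December 2019, still carries both commitments, so the protocol has not withdrawn them.

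**2. Does the markedly abnormal table supply the baseline?**

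Attachment 3 shows 19 criteria in the text available, which may be cut off after calcium. Fifteen require a change from baseline as well as an absolute value. The four that do not are hematocrit, total WBC, chloride and total protein. An unchanged entry abnormality cannot trigger any of the fifteen, but their cuts are extreme:

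- Hemoglobin must fall by more than 20 g/L and be below 100 g/L. From the entry floors that means below 80 − 20 = 60, 85 − 20 = 65 or 90 − 20 = 70 g/L. A child entering at 80 to 99 g/L is already under the absolute limit.
- ALT must at least double and exceed 150 U/L. The entry limits of 41 and 52 IU/L at 1.2 × ULN imply ULNs of 41/1.2 = 34.2 and 52/1.2 = 43.3. The cut of 150 is then 150/43.3 = 3.5 to 150/34.2 = 4.4 times ULN.
- Three times ULN is about 103 to 130 U/L, below 150. In the sponsor's subcutaneous study (protocol 1.1.2.2), 39 of 51 children with abnormal ALT (76%) stayed under 3 × ULN. On the ULNs implied here, elevations of that size would not reach the markedly abnormal table.

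**3. Do the other displays?**

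The ALT/AST summary by TB prophylaxis is post-baseline but shows no baseline value. The boxplots include baseline, but they show group distributions for six analytes and do not follow a child from one class to another.

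**4. How carry-in acts in the maximum-grade table**

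Let b be the share abnormal at entry and persisting, and t the rate of new abnormality among the rest.

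Unadjusted proportion = b + (1 − b)t; newly abnormal = (1 − b)t; difference = b.

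The documents give neither b nor t. For illustration only, with 120 children and t = 10%:

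| b | Unadjusted | Children with a grade | Carried in |
|---|---|---|---|
| 5% | 0.05 + 0.95 × 0.10 = 14.5% | 17.4 | 6 |
| 10% | 0.10 + 0.90 × 0.10 = 19.0% | 22.8 | 12 |
| 20% | 0.20 + 0.80 × 0.10 = 28.0% | 33.6 | 24 |
| 30% | 0.30 + 0.70 × 0.10 = 37.0% | 44.4 | 36 |

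This assumes that grading starts just outside the normal range. SAP 6.3 implies that normal ranges are used for grading, but the CTCAE cut-points are not reproduced.

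**The case against.** The strongest reply is that the SAP already controls for baseline where it matters. Three laboratory displays stand beside the maximum grade, one of them showing baseline values and another defined mainly by change from baseline. SAP 6.2 also lists hepatobiliary events at ALT of at least 3 × ULN with raised bilirubin or a hepatobiliary serious event, well above the entry limit. Exclusion criterion 19 removes children with persistent ALT and AST elevation (more than 3 of 5 tests in six months) and clinically significant marrow suppression, and criterion 15 sets floors for white cells, neutrophils and platelets. Transaminase carry-in at screening is thus confined to a band up to 1.2 × ULN. Any carry-in raises the apparent rate rather than hiding harm, and nothing is tested.

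All of that stands, and it limits the point to the maximum-grade table and to milder abnormalities. It does not supply the subject-level comparison that protocol 11.7 promised.

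A reader might go further than the documents allow in three ways:

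- That the SAP reports nothing but maximum grades. It does not; the other displays are specified.
- That the SAP counts entry abnormalities as treatment-emergent toxicity in its main laboratory table. It applies the term treatment-emergent to adverse events only and ranks no laboratory table as main.
- That the SAP deliberately substituted one table for the other. No text withdraws the cross-tabulation; it is simply absent.

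**Conclusion.** The point holds as an omission with a limited consequence. SAP 6.3 lacks two laboratory displays that the current protocol still promises. Its maximum-grade summary cannot separate abnormalities present at entry from new or worsened ones, and does not say the maximum is post-baseline.

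The size cannot be determined from the documents. The excess equals b, which they do not report, so the illustrative table shows the mechanism and is not an estimate. It is tempting to take a size from the subcutaneous study, but its 29.5% with abnormal ALT is an on-study rate, not a baseline rate. The fraction printed with it, 51/167, is 30.5%; 51/173 gives 29.5%. Protocol 1.1.2.2 says of the two children above 8 × ULN that "one of the subjects had baseline ALT which was already abnormal". A rise to that level is real worsening, which a shift table would still count, so the case shows that entry abnormality occurs but not that a rate was inflated.

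The conclusion rests on the grading assumption stated above and on Attachment 3 as far as it can be read. It should be corrected before the tables are programmed, and it does not affect the primary PK endpoints.

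**What to change.** In SAP 6.3:

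- State that the maximum grade is the worst post-baseline grade.
- Keep that summary and add, for the same parameters, a shift table of baseline CTCAE grade by worst post-baseline grade. Report the proportion of children whose grade rises above baseline.
- Restore the protocol 11.7 cross-tabulation by normal-range class and the listing of children with markedly abnormal results.

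The maximum-grade summary need not be removed; the shift table supplies what it lacks. The cost is a few sentences in the SAP and a few table and listing shells. Laboratory samples are already scheduled at screening, Week 0 and later visits, so no new data are needed.

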6.4. Vital Signs and Physical Examination Findings

Vital signs including heart rate, respiratory rate, temperature, and blood pressure (systolic and diastolic) values and changes from baseline will be summarized by visit.

6.5. Electrocardiogram

This section does not apply to this study.

6.6. Antinuclear (ANA)/ Anti-dsDNA antibodies

Blood samples will be collected at Weeks 0, 24, 52, 76, 100, 124, 148, 172, 196, 220 and 244 to determine the presence of antinuclear (ANA)/ anti-dsDNA antibodies.

Subjects' baseline ANA and anti-dsDNA status and proportion of subjects who change ANA and anti-dsDNA status during the trial will be summarized.

7. PHARMACOKINETICS/PHARMACODYNAMICS AND IMMUNOGENICITY

7.1. Pharmacokinetics

7.1.1. Primary PK Endpoints

The primary endpoints in this study are PK exposure at Week 28 (the trough concentrations at Week 28) and the Bayesian AUC_{ss} over one dosing interval of 8 weeks (from population PK modeling and simulation).

7.1.1.1. Definition

C_{trough,wk28}: Serum golimumab trough concentration at Week 28

AUC_{ss}: Area under the curve at steady-state over a dosing interval

7.1.1.2. Analyses Methods

Summary golimumab concentrations will be summarized and PK exposure will be evaluated through Week 52 and through the LTE (Week 252).

A population PK analysis with data through Week 28 will be performed to characterize the PK of golimumab as well as to identify and quantify important covariates of PK in the pediatric population with JIA. Clearance and volume of distribution will be estimated using a nonlinear mixed effects modeling (NONMEM) approach. Details will be provided in a population PK analysis plan and the results of the analysis will be presented in a separate report.

Measures of PK exposure will be graphically evaluated in the pediatric populations after administration of IV golimumab (including but not limited to steady-state C_{max}, C_{min} and AUC) and compared to PK exposure from adults in CNTO148ART3001. Similarity between pediatric and adult subjects will be assessed by the generation of box plots from the population PK modeling via visual inspection in addition to the descriptive statistics of the observed concentrations.

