3.2.2. Dose Selection

Unlike adult drug doses, pediatric drug doses (parenteral) are commonly calculated individually as weight-based (mg/kg) or BSA-based (mg/m²) doses to manage the PK variability observed in children across different ages as changes occur in their maturing organ systems. 10,22 The successful outcome of dose extrapolation from adults to pediatric subjects through weight-based or BSA-based dose normalization for other approved anti-TNF α agents (eg, adalimumab and etanercept) supports the assumption that clinical responses to anti-TNF α agents in rheumatoid disease would be similar between adults and children. That is, after the PK differences inherent

between adults and children are accounted for, similar drug responses would be expected with similar drug exposure in both adults and children.

Data from the Phase 3 IV study in adults with RA (CNTO148ART3001) through 24 weeks have shown that golimumab 2 mg/kg at Week 0, Week 4, and q8w (±1 week) thereafter is the optimal dose regimen for the treatment of RA in most adults. For a child, golimumab 80 mg/m² (2 mg/kg/1.73 m²) would be approximately equivalent to 2 mg/kg for an adult subject weighing 70 kg (with a BSA of 1.73 m²). Thus, in the current study (CNTO148JIA3003), a dose of golimumab 80 mg/m² has been chosen to evaluate the safety and efficacy of golimumab in the pJIA population.

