3.2.3. Rationale

The open-label study design for IV golimumab in the pJIA population is based on data from studies of other anti-TNF α agents in adult RA and pJIA, PK and efficacy data from the Sponsor's study of IV golimumab in adult RA (CNTO148ART3001), the Sponsor's experience with SC golimumab in pJIA (CNTO148JIA3001), and feedback from the Pediatric Rheumatology International Trials Organisation (PRINTO) and The Pediatric Rheumatology Collaborative Study Group (PRCSG).

The Sponsor will utilize PK data generated from the proposed open-label CNTO148JIA3003 study to extrapolate to adult PK data from the CNTO148ART3001 study in RA, which was the pivotal study that served as the basis for approval of IV golimumab (SIMPONI ARIA/SIMPONI for Intravenous Use) for adult patients with RA. Additionally, efficacy (PD) data will be collected to explore the assessment of supportive exposure-response.

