9.3.3. Pharmacokinetic Parameters

Serum golimumab concentrations will be evaluated at Weeks 0, 4, 8, 12, 20, 28, 52, 100, 148, 196, and 244 and summarized over time.

Pre-infusion (immediately before infusion) and post-infusion (1 hour after infusion) samples will be drawn at Weeks 0, 4, and 12, and an additional random population PK sample will be drawn at any time between Weeks 0 and 8 other than at the time of the Week 0, Week 4, and Week 8 visits and collected at least 24 hours prior to or after study agent administration. For each of the remaining visits, only 1 sample for serum golimumab will be collected, which should be collected prior to the infusion if an infusion of the study agent is administered at that visit. Post-infusion samples should be drawn from a different arm than the IV infusion line, or the IV infusion line must be flushed and cleared of any residual medication that may be remaining and 1 mL of blood should be drawn and discarded prior to obtaining the sample if using the same access line as was used for drug administration.

A population PK analysis with data through Week 28 will be performed to characterize the PK of golimumab as well as to identify important covariates of PK in the pediatric population with pJIA. Additionally the population PK model will be used to assess the similarity of the PK in pediatrics and adults. The clearance and volume of distribution will be estimated using a NONMEM approach. In addition, an exposure-response analysis will be performed to explore and characterize the relationship between exposure and efficacy.

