11. STATISTICAL METHODS

Statistical analysis will be done by the Sponsor or under the authority of the Sponsor. A general description of the statistical methods to be used to analyze the efficacy and safety data is outlined below. Specific details will be provided in the Statistical Analysis Plan.

In general, descriptive statistics, such as mean, median, standard deviation, interquartile range, minimum and maximum for continuous variables, and counts and percentages for categorical variables will be used to summarize data.

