11.4. Pharmacokinetic Analyses

The primary objective of this study is to characterize golimumab PK exposure (the trough concentrations at Weeks 28 and the Bayesian AUCss over a dosing interval of 8 weeks from population PK modeling and simulation) in the pJIA population.

Serum golimumab concentrations will be summarized over time. In addition, a population PK analysis on data through Week 28 will be performed to characterize the PK of golimumab as well as to identify and quantify important covariates of PK in the pediatric population with pJIA. Clearance and volume of distribution will be estimated using a NONMEM approach. Details will be provided in a population PK analysis plan and the results of the analysis will be presented in a separate report.

Measures of PK exposure will be graphically evaluated in the pediatric populations after administration of IV golimumab (including but not limited to steady-state C_{max} , C_{min} and AUC) and compared to PK exposure from adults in CNTO148ART3001. Similarity between pediatric and adult subjects will be assessed by the generation of box plots from the population PK modeling via visual inspection in addition to the descriptive statistics of the observed concentrations.

Summary golimumab concentrations will be summarized and PK exposure will be evaluated through Week 52 and through the LTE.

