1.4. Sample Size Justification

The sample size determination is not based on statistical considerations. For the purpose of determining sample size of this study, the variability of PK in pediatric populations was considered. The goal is to have a sample size that will be sufficient to build a population PK and, if feasible, an exposure-response model. Additionally, a sample size that will provide information about the safety profile of golimumab IV in children was also taken into consideration.

With these considerations, a sample size of approximately 120 subjects has been chosen assuming that if 20 subjects were to drop out or if they do not provide PK samples, a sample size of approximately 100 subjects is thought to be sufficient to build a population PK model, given the sparse sampling of PK time points, as well as provide 1 year of safety data from approximately 100 subjects.

Assuming that inter-subject coefficient of variation (CV%) of concentration is about 50% (moderate – large variation), a sample size of 100 subjects will be able to provide a 95% confidence interval (CI) with the length about 20% of the mean concentration, i.e., 95% CI \approx Mean×(1 \pm 10%).

The table below provides the length of 95% CI of mean concentration using sample size of 100 subjects with various CV% from 30% (small variation) to 70% (larger variation).

CV %	95% CI
30%	Mean×(1± 5.9%)
40%	Mean×(1± 7.8%)
50%	Mean×(1± 9.8%)
60%	Mean×(1±11.8%)
70%	Mean×(1±13.7%)

Table 1: Length of 95% CI with Sample Size 100 Subjects

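### Pediatric-adult PK similarity, which supports the adult extrapolation, is judged by eye: neither document specifies a pediatric:adult estimate with its uncertainty

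*SAP*

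**What the plan says.** SAP 7.1.1.2 introduces the comparison with "Measures of PK exposure will be graphically evaluated in the pediatric populations after administration of IV golimumab", covering at least steady-state Cmax, Cmin and AUC, against adults in CNTO148ART3001. Similarity is then judged from "box plots from the population PK modeling via visual inspection in addition to the descriptive statistics of the observed concentrations". Protocol 11.4 agrees: "Similarity between pediatric and adult subjects will be assessed by the generation of box plots". Protocol 9.3.3 adds that "the population PK model will be used to assess the similarity of the PK in pediatrics and adults", without naming a quantity to be estimated.

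The role of the comparison is set out in the rationale. Protocol 3.2.2 reasons that "similar drug responses would be expected with similar drug exposure in both adults and children", and Protocol 3.2.3 says the PK data will be used "to extrapolate to adult PK data from the CNTO148ART3001 study in RA".

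For summaries in general, Protocol Section 11 names "descriptive statistics, such as mean, median, standard deviation, interquartile range, minimum and maximum for continuous variables". The output list in SAP 7.1.3 covers pediatric concentrations by visit and subgroup, with no interval and no adult comparison. The only confidence interval discussed in either document is in SAP 1.4, for the pooled pediatric mean concentration with 100 subjects. Both documents state that no formal hypothesis test is planned, and both leave population PK details to a separate analysis plan.

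**The concern.** In a single-arm study without a concurrent control, the comparison with adult exposure is the link to the adult efficacy data. A box plot shows a median and the spread between subjects. It does not show the uncertainty of the difference between two groups. A reader could work out a rough trough difference from the descriptive statistics, but AUCss is model-derived, so descriptive statistics of observed concentrations do not cover it.

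The problem is sharpest in the youngest children, expected to be about a tenth of the sample. With so few, two boxes can look alike or different by chance. These children are also furthest in size from the adult of 70 kg and 1.73 m² that Protocol 3.2.2 uses to derive the mg/m² dose.

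**Working it through.** **Inputs**
- CV of concentration 50%, range 30% to 70%; 100 evaluable subjects (SAP 1.4).
- Age mix of about 10%, 20% and 70% for 2 to <6, 6 to <12 and 12 to <18 years (Protocol 3.1), giving about 10, 20 and 70 of 100.
- Adults: 592 randomized 2:1 to golimumab or placebo (Protocol 1.1.2.1), so 592 × 2/3 ≈ 395 on golimumab. The number with usable PK data is not given, so 200 is also tried.

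**Step 1: reproduce SAP Table 1.** Half-width = 1.96 × CV / √100. For CV 30, 40, 50, 60 and 70% this gives 5.88, 7.84, 9.80, 11.76 and 13.72%, matching the printed 5.9, 7.8, 9.8, 11.8 and 13.7%.

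**Step 2: the same formula by age group**, half-width = 1.96 × CV / √n:

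| Group | n | CV 30% | CV 50% | CV 70% |
|---|---|---|---|---|
| All | 100 | ±5.9% | ±9.8% | ±13.7% |
| 12 to <18 years | 70 | ±7.0% | ±11.7% | ±16.4% |
| 6 to <12 years | 20 | ±13.1% | ±21.9% | ±30.7% |
| 2 to <6 years | 10 | ±18.6% | ±31.0% | ±43.4% |

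With t(9) = 2.262 in place of 1.96, the youngest group at CV 50% becomes 2.262 × 0.50 / √10 = ±35.8%.

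**Step 3: illustrative precision of a pediatric:adult geometric mean ratio.** Assume log-normal exposure, equal CV in both groups and independent samples. Then SD on the log scale = √ln(1 + CV²) = 0.294, 0.472 and 0.632 for CV 30, 50 and 70%. The 95% interval is the ratio multiplied and divided by exp(1.96 × SD × √(1/n + 1/395)).

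| Group | n | CV 30% | CV 50% | CV 70% |
|---|---|---|---|---|
| All | 100 | 1.067 | 1.109 | 1.149 |
| 12 to <18 years | 70 | 1.077 | 1.128 | 1.174 |
| 6 to <12 years | 20 | 1.141 | 1.236 | 1.328 |
| 2 to <6 years | 10 | 1.202 | 1.345 | 1.486 |

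At CV 50%, an observed ratio of 1 would carry a 95% interval of 0.90 to 1.11 overall and 0.74 to 1.35 in the youngest group. At the 90% level the factors are 1.09 and 1.28. With 200 adults the 95% factors are 1.120 and 1.350, so the adult count hardly matters.

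**The case against.** The strongest objection is that the population PK analysis plan was not available. Both documents send model details there, AUCss comes from that model, and a ratio with model-based uncertainty could well be specified in it. This stands as a limit: the gap is shown for the protocol and SAP only.

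Other points have some force:
- The model will also quantify covariate effects such as age and weight, which inform the youngest children. That is not a direct pediatric:adult contrast.
- Neither document says that the adult comparison will be split by age. The SAP 2.4.1 age groups are for pediatric concentration summaries, so the by-age comparison is part of the recommendation.
- The lists of statistics are open, so intervals are not excluded. They are not specified either.
- The figure of 10 young children comes from the 100 expected at Week 52. With 10% of the 120 enrolled, n = 12 and the Step 2 half-width is 1.96 × 0.50 / √12 = ±28.3%, still wide.
- A population model shares information across ages, so the stand-alone subgroup formula is not the precision that the model would give.
- No formal test is planned, no stated decision rule depends on similarity, and efficacy is observed directly. This lowers the stakes, but an estimate with an interval is compatible with a descriptive aim.

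**Conclusion.** The concern holds. The protocol and SAP rest similarity on inspection of plots and descriptive statistics, and neither specifies a pediatric:adult estimate with its uncertainty.

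On the SAP's own CV, uncertainty is modest for the pooled sample (about ±10% for the mean) and roughly three times as large in the 2 to <6 year group. The Step 2 figures assume that the expected age mix is achieved. The ratio figures also apply a concentration CV to AUCss and to adults, and take an adult count that the documents do not confirm. They show scale only, and the gap does not depend on them. This is a reporting weakness worth correcting. It does not make the planned analysis invalid.

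**What to change.** In SAP 7.1.1.2, keep the box plots and descriptive statistics and add:

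1. The pediatric:adult geometric mean ratio with a confidence interval for AUCss and model-derived steady-state trough, overall and in the three age groups of SAP 2.4.1. Take the interval from the population PK model so that it reflects parameter uncertainty. If individual Bayesian estimates are used instead, report shrinkage. A 95% level would match SAP 1.4.
2. The percentage of children within the adult 5th to 95th percentile range.
3. The pediatric mean Week 28 trough with the 95% interval that SAP 1.4 uses to support the sample size.

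Item 1 answers the concern. Items 2 and 3 are useful but secondary. If the population PK plan already contains items 1 and 2, cross-refer to it. No hypothesis test or similarity bound is required.

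The cost is a few table rows from data and model output already planned. The drawback is a visibly wide interval for the youngest group.
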